## 7.3. Study intervention administration

### 7.3.1. Ovarian stimulation

At Visit 2, eligible patients will be randomized to the DPOS group or GnRH antagonist group:

**For DPOS arm (Group I):** Patients will be co-administered with Human Menopausal Gonadotrophin (HMG) 225 IU/day (IU/d) via intramuscular injection and oral DYG (Duphaston) 30mg/d from menstrual cycle day 2 - 4 (CD2 – CD4) (**Visit 2**) to the day of final oocyte maturation (Dual trigger with Ovitrelle 250 mcg and Diphereline 0,2mg).

**For GnRH antagonist arm (Group II):** In the fixed GnRH antagonist protocol, daily s.c. administration of GnRH antagonist (Ganirelix 0.25 mg) will be initiated on the 5th day of stimulation. HMG 225 IU will be administered daily from menstrual cycle day 2 - 4 (CD2 – CD4) (**Visit 2**), and follicular monitoring will be performed after 4 days of

injections. Treatment with HMG and GnRH antagonist will continue daily until the day when final oocyte maturation is triggered (Dual trigger with Ovitrelle 250 mcg and Diphereline 0,2mg)

Follicular development will be monitored by ultrasound scanning and measurement of LH, E2 and P4 on Day 5 (**Visit 3**) and Day 8 (**Visit 4**). Scanning and hormonal measurement will be repeated depending on the size of the follicles. A dual trigger with Ovitrelle 250 mcg and Diphereline 0,2mg will be used when at least one leading follicles of 17 mm (**Visit 5**). After 12 hours of final maturation injection, hormonal measurement also will be performed (**Visit 6**).

#### *7.3.2. Oocyte retrieval and cryopreservation*

After 36 hours of final maturation injection (**Visit 7**), all follicles greater than 12mm in diameter will be aspirated. In the low ovarian reserve group, oocyte cryopreservation will be applied to collect at least  $7 \pm 1$  oocytes. The patient will be stimulated with the previous OS protocol for the following ovarian stimulation cycle. The visits of the patient will be repeated as the first OS cycle.

Oocytes will be received after 36 hours post-hCG. Then, the cumulus-oocyte complexes (COCs) will be cultured for 2 hours in a CXCM medium (Irvine, USA) (37oC, CO2 6%, O2 5%). After 2 hours, the oocytes will be denuded, and the presence of the first polar body will assess oocyte maturity.

Matured oocytes will be frozen by vitrification (CRYOTEC® Method) (39). Firstly, the oocytes will be balanced in an equilibration solution (ES). When the shape of the oocyte fully recovers, it will be transferred to a Vitrification Solution (VS) with a minimum equilibrium (the limit time is 15 min). The oocyte will be exposed to a vitrification solution by maintaining the same mixture of cryoprotectants but double-concentrated for 50 – 60 seconds. Loading takes place within the next 10 seconds by placing oocytes on the device contained in the minimum volume—immediately plunging into liquid nitrogen-induced vitrification. Three oocytes maximum will be loaded per device container. Oocytes were stored in liquid nitrogen tanks for a variable storage time.

#### *7.3.3. Oocyte thawing and ICSI*

For the last ovarian stimulation cycle, based on the aim to collect at least  $7 \pm 1$  oocytes, the clinician will determine the last ovarian stimulation cycle on the day of final oocyte maturation. It is defined as a cycle in that the total number of frozen and expected fresh oocytes is more than seven. The patient will be stimulated with the previous OS protocol. The visits of the patient will be repeated as the first OS cycle. However, the frozen oocytes of the previous OS cycle will be thawing; all fresh and frozen oocytes will be fertilized by ICSI at **Visit 7**.

For the fresh oocyte, the oocytes will be received after 36 hours post-hCG. Then, the cumulus-oocyte complexes (COCs) will be cultured for 3 hours in a CXCM medium (Irvine Scientific., USA) (37oC, CO2 6%, O2 5%). After 3 hours, the oocytes will be denuded, and oocyte maturity will be assessed by the presence of the first polar body and continued to culture for another hour before ICSI.

The thawing process will follow the CRYOTEC® Method (39). After removing the liquid nitrogen, the oocytes will be transferred immediately into the 37oC thawing solution (TS) within 1 minute. Then the oocyte will be transferred to a diluent solution (DS) for 3 minutes at room temperature. The warming procedure will be completed using two washes (one lasting 5 minutes, the other 1 minute) in the buffer solution at room temperature. After warming, oocytes were placed under standard culture conditioners at 6%CO2 and atmospheric at 37°C for 2 hours before the intracytoplasmic sperm injection. After warming, the survival oocyte is evaluated. Warmed oocytes are considered

'morphologically surviving' if there is no dark/degenerated or contracted ooplasm and no cracked zona pellucida. Oocytes with an abnormal oolemma or ooplasm at the time of ICSI should not be excluded (40) Semen samples will be obtained by masturbation after 3–5 days of ejaculatory abstinence. After the samples are liquefied at room temperature, a semen analysis will follow the WHO (2021) guidelines (41). The density gradient procedure will use the Isolate (Irvine Scientific., USA) discontinuous density gradient. Briefly, one aliquot of liquefied semen will be loaded onto 40%, and 80% gradients (each 1.0 ml) with the 80% fraction at the bottom of a 15 ml tube and then will be centrifuged at 300 g for 10 min at room temperature. After centrifugation, the sperm pellet will be washed twice in 3 ml of pre-warmed MHMC [Irvine Scientific., USA] and centrifuged for 5 min at 300 g. The supernatant will be discarded, and the final pellet will be resuspended in a pre-warmed MHMC medium.

Intracytoplasmic sperm injection (ICSI) is performed at 40 hours post-hCG for both the fresh and frozen oocytes and continues to culture in the CXCM medium (Irvine Scientific., USA) (37oC, CO2 6%, O2 5%). Once injected, oocytes were placed in the individual wells. Wells will be filled with 20ul of CXCM medium (Irvine, USA) (37oC, CO2 6%, O2 5%). Fertilization check at 17±1 hours post-ICSI and only normally fertilized zygotes show two pronuclei (2PN) are continued to culture to day 3. The morphology of culture embryos will be assessed at 68±1 hours, 116±2 hours, and 140 ± 2 hours after injection. The evaluated parameters include cell number, symmetry, and percentage of fragmentation for cleavage day 3. Cleavage day 3 embryos with greater than 6 blastomeres will be considered day 3 embryos. All embryos are continued to culture until day 5.

On day 5, the quality of blastocysts will depend on the expansion of the blastocoele cavity and the integrity of both the inner cell mass and trophectoderm cells. Embryos are categorized into four grades (Grade 1: AA, AB, BA, Grade 2: BB, Grade 3: BC, CB, and Grade 4: others). The highest-graded blastocysts with a blastocoel expansion greater than 3 (42) are vitrified (CRYOTEC® Method). The slow-growing embryos (the blastocoel expansion lesser than 3, cleaved embryos) continue to culture to day 6.

On day 6, the blastocysts are assessed and vitrified similarly to day 5 embryos. Freeze all in both arms, then the frozen embryo will be transferred in the next cycle.

#### *7.3.4. Embryo cryopreservation*

At **Visit 8**, after 5-6 days of culture, all embryos are cryopreserved by vitrification ( one embryo/container) using CRYOTEC® Method. We will be frozen blastocysts that have the expansion of grade 3 or more, and the quality of the inner cell mass and trophectoderm cells have grade B or C (not used for CC). The procedures for oocytes will be similar to those described above, such as the vitrification step, loading, and storage. Firstly, the embryos will be balanced in an equilibration solution (ES). When the shape of the embryos is fully recovered, they will be transferred to a Vitrification Solution (VS) with a minimum equilibrium (the limit time is 15 min). The embryos will be washed in the VS2 well and spread onto the Cryotec (one blastocyst/Cryotec). After freezing, the containers will be stored in liquid nitrogen.

#### *7.3.5. Endometrium preparation and embryo transfer*

At **Visit 9**, all patients undergoing FET will receive oral estradiol valerate (Valiera®; Laboratories Recalcine) 6 mg/day from the 2nd to 4th day of menses for 6 days. The endometrial thickness will be monitored from day six onwards. From day 8-9 of menses, the estradiol dose could be adjusted to 12mg/day according to the development of the

endometrium. Progesterone will be started when endometrial thickness reaches 8 mm or more. Patients will receive micronized Progesterone (Cyclogest® 400mg; Actavis) at the dose of 400mg twice daily (morning and evening) plus dydrogesterone (Duphaston 10mg) at the dose of 10mg twice daily (morning and evening). Estradiol valerate will be decreased to 4 - 8mg/day when starting Progesterone. A single embryo will be thawed on the day of embryo transfer after six or seven days of Progesterone, depending on day-5 or day-6 embryo. After thawing, surviving embryos will be transferred into the uterus under ultrasound guidance. Estradiol and Progesterone will be continued until the day of the pregnancy test. If the pregnancy test is positive, the patients will continue to use 800 mg micronized Progesterone or 800 mg micronized Progesterone plus 20 mg dydrogesterone until 7 weeks of gestation. The blastocyst will be thawed on embryo transferring day (**Visit 10**) according to the CRYOTEC® Method. After warming, the survival blastocyst is evaluated. Blastocyst cryo-survival be defined as at least 75% of cells perceived to be intact after thawing (40). After thawing, the embryo will be cultured in a CXCM medium (37oC, CO2 6%, O2 5%). The embryo will be transferred to the uterus two hours later under ultrasound.

#### 7.3.6. *Quality of life assessment*

These participants completed questionnaires, which included a standardized quality of life measure (World Health Organisation Quality of Life -- Brief Assessment (WHOQoL-BREF)). The WHOQoL-BREF assesses four domains of quality of life: 1) physical 2) psychosocial 3) social relationships, and 4) environment.

The total score will be converted to a 100-point scale (according to WHO guidelines). The questionnaire will be assessed at two points:

- On the Day 2 of menstruation in the first cycle (**Visit 1**)
- On the day of the final maturation injection of last OS cycle (**Visit 6 of the last cycle**)

### 7.4. Study intervention follow-up

#### 7.4.1. *Ovarian hyperstimulation syndrome assessment.*

In low ovarian reserve patients, the risk of OHSS is rare. However, following oocyte retrieval, if the number of collected oocytes is more than 20 with an hCG trigger, they will be managed according to the OHSS management policy of IVFTA HCM. In short, the high-risk patient will be documented and educated regarding symptoms and when to seek further help. Clinical examination on the Day 3 and Day 5 of embryo culture in person is mandatory for all high-risk OHSS cases (**Visit 8**).

OHSS diagnosis accords with RCOG guideline 2016. The category of OHSS severity is listed in Table 1. Outpatient management is applied for women with mild and moderate OHSS. Hospital admission will be considered when having severe or critical OHSS symptoms requiring paracentesis. Severe OHSS is an SAE and will be reported.

**Table 1.** Category of Ovarian hyperstimulation syndrome severity

Category	Features
Mild	Abdominal bloating Mild abdominal pain Ovarian size usually < 8 cm3
Moderate	Moderate abdominal pain Nausea ± vomiting Ultrasound evidence of ascites

	Ovarian size is usually 8 - 12 cm 
Severe	Clinical ascites ( $\pm$ hydrothorax). Oliguria (< 300 ml/day or < 30 ml/hour) Hematocrit > 45% Hyponatraemia (Na + / máu < 135 mmol/l) Hypo-osmolality (osmolality < 282 mOsm/kg) Hyperkalaemia (K + > 5 mmol/l) Serum Albumin (< 35 g/l) Ovarian size usually > 12 cm
Critical	Tense ascites/ large hydrothorax Hct > 55% White cell count > 25 000/ml Oliguria/ Anuria Thromboembolism ARDS (Acute Respiratory Distress Syndrome)

Note: Hct = haematocrit; WBC = white blood cell; CrCl = creatinine clearance; Cr = creatinine; Na+ = sodium; K+ =potassium
 
Ovarian size may not correlate with the severity of OHSS in cases of assisted reproduction because of the effect of follicular aspiration
	

#### 7.4.2. *Pregnancy outcome follow-up*

Serum hCG will be measured 11 days after embryo transfer (**Visit 11**), and if positive, an ultrasound scan of the uterus will be performed at gestational weeks 7 (**Visit 12**) and 12 (**Visit 13**). At 11–12 weeks of gestation, participants will be referred to the IVFTA HCM - Tam Anh TP. Ho Chi Minh General hospital and IVFTA – Tam Anh General hospital for prenatal care. For those who cannot participate in the prenatal care program at Tam Anh TP. Ho Chi Minh General hospital or Tam Anh General hospital, for any reason, will contact the participants via telephone/email to collect data. We also ask these participants to scan the results of each visit in every contact.

## 8. OUTCOME MEASUREMENTS

The primary endpoint is ongoing pregnancy after the first embryo transfer. Ongoing pregnancy is defined as pregnancy with a detectable heart rate at 12 weeks' gestation or beyond after the completion of the first transfer. Cycles in which no blastocyst is available for transfer will be considered failures. Several fertility outcomes, characteristics, and outcomes of the ovarian stimulation, patient safety, drop-out rate, and quality of life during oocyte accumulation will be assessed as secondary endpoints. Full details and definitions are provided in Table 2.

**Table 2.** Secondary endpoints and their definition

Secondary endpoints	Definition
LH, Estradiol and progesterone profile	LH, Estradiol, and progesterone level are measured on day 1, day 5, and day 8 of ovarian stimulation, final oocyte maturation day, and 12 hours after the final oocyte maturation injection
Rate of premature LH surge	Premature LH surge (PLS) is increased serum LH more than twice the baseline or more than 15 mIU/ml

	The rate of Premature LH surge is defined as number of PLS appearances per number of ovarian stimulation cycles
Duration of ovarian stimulation	Number of ovarian stimulation days (from the first day of FSH injection to final oocyte maturation injection day)
The total dose of FSH	A number of international units of HMG are administrated during ovarian stimulation
Number of Cumulus-oocyte complex (COCs)	Number of Cumulus-oocyte complexes after oocyte retrieval
Number of MII oocyte	Number of MII oocytes after denuding
Number of survival oocyte	Number of survival oocytes after thawing
Fertilization rate per oocyte inseminated/injected	Fertilisation is defined as the appearance of two PN at 17±1 hour per inseminated/injected
Embryo-cleavage rates	Number of embryos on Day 3 after ICSI day
Blastocyst rate	Numbers of embryos on Day 5 and Day 6 after ICSI
Number of survival blastocyst	Number of survival embryos on Day 5 and Day 6 after thawing
Top-quality blastocyst rate	Numbers of embryos on Day 5 and Day 6 with good quality after ICSI
Positive pregnancy test	A positive pregnancy test is defined as a serum hCG level greater than 25 mIU/mL 11 days after the first transfer
Implantation rate	Implantation rate is defined as the number of gestational sacs per number of embryos transferred 3 weeks after the first transfer
Biochemical pregnancy	Biochemical pregnancy is defined as a pregnancy diagnosed only by the detection of beta hCG in serum or urine
Miscarriage	Complete loss of clinical pregnancy at 12 weeks of gestation
Multiple pregnancy rate	Multiple pregnancy rate is explained as two or more gestational sacs or positive heartbeats by transvaginal sonography 5 weeks after embryo placement
Ectopic pregnancy rate	Ectopic nidation of pregnancy confirmed by sonography or laparoscopy at 12 weeks of gestation
OHSS	Ovarian hyperstimulation is diagnosed according to RCOG guideline 2016
Known Adverse events regarding medications	
Adverse events regarding medications according to local information products - including:
 
 
• Duphaston: Abdominal pain, bloating, severe headache, dizziness, depression, hot flushes, abnormal vaginal discharge, joint pain, urinary problems or nausea, fatigue or extreme tiredness, somnolence or sleepiness, vaginal hemorrhage, pruritus (severe itching of the skin).
 
• Orgalutran: redness, pain or swelling at injection site, headache, nausea, tiredness.
 

	
 
• Diphereline: nausea, tiredness, mood changes, depression, redness, swelling, pain and /or bruising at the injection site, swelling of the hands and feet (edema) muscle and bone pain, pain in arms and legs, dizziness, headache, impotence, loss of libido.
 
• Ovitrelle: injection site, headache, vomiting, nausea (feeling sick), abdominal (belly) pain, abdominal distension (feeling of bloating)
 
• Valiera: Headache, nausea, breast pain, abdominal cramp, bloating, vaginal spotting.
 
• Cyclogest: Abdominal distension (swelling in the abdomen), abdominal pain, constipation, sleepiness, tiredness, hot flush, breast pain.
 
• IVF-M: Headache, injection site pain, injection site allergic reaction, abdominal pain, abdominal cramps or nausea.
 

Drop-out	Drop-out is defined as any patient discontinuing the Study or the investigator withdrawing them from the Study for any reason.
Quality of life score	Quality of life is assessed by Vietnamese WHO-BRIEF questionnaire

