##### 4.2. Secondary objectives:

- To compare the characteristics of ovarian stimulation between DPOS and GnRHanta protocol, including LH, Estradiol, and Progesterone profile (Day 1, day 5, and day 8 of ovarian stimulation, final oocyte maturation day, and 12 hours after the final oocyte maturation injection), premature LH rate, the duration of ovarian stimulation and the total dose of FSH, the number of ovarian stimulation cycles.

- To compare the outcomes of the ovarian stimulation between DPOS and GnRH protocol, including number of cumulus-oocyte complexes, number of MII oocytes, oocyte survival rate, fertilization rate, embryo-cleavage rate, blastocyst rate, top-quality blastocyst rate, blastocyst survival rate, implantation rate, positive pregnancy rate, clinical pregnancy rate, early miscarriage rate, multiple pregnancy rate, ectopic pregnancy rate.
- To compare the drop-out rate of DPOS and GnRH protocol in accumulation oocyte cycles of patients with low ovarian reserve
- To assess the safety of DPOS and GnRH protocol in accumulation oocyte cycles of patients with low ovarian reserve.
- To compare the quality of life during ART treatment based on WHO-BRIEF questionnaire

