- **Visit 6** (1st cycle - Day  $11 \pm 2$  of OS): blood sampling (for hormone check-up) will be performed after 12 hours of final oocyte maturation injection.
- **Visit 7** (1st cycle - Day  $12 \pm 2$  of OS): Oocyte retrieval and oocyte cryopreservation will be performed. AE/SAE will be recorded routinely.

*For the following ovarian stimulation cycle (s):* the patient will be stimulated with the previous OS protocol. The visits of the patient will be repeated as the first OS cycle.

*For the last ovarian stimulation cycle:* Based on the aim to collect at least  $7 \pm 1$  oocytes, the clinician will determine the last ovarian stimulation cycle on the day of final oocyte maturation. It is defined as a cycle in that the total number of frozen and expected fresh oocytes are at least  $7 \pm 1$  oocytes. The patient will be stimulated with the

previous OS protocol. The visits of the patient will be repeated as the first OS cycle. However, the frozen oocytes of the previous OS cycle will be thawed. All fresh and thawed oocytes will be fertilized by ICSI at **Visit 7**.

- **Visit 8:** (Day 77 ± 7 – Embryo culture report): The patient will receive a Blastocyst embryo culture report and decide whether embryo cryopreservation or not.
- **Visit 9:** (Day 90 ± 7 – Endometrial preparation): Endometrial preparation will start on the 2nd – 4th of mense.
- **Visit 10:** (Day 109 ± 7 – Embryo transfer): Progesterone will be started when endometrial thickness reaches 8 mm or more for 6 - 7 days. Embryo transfer will be performed under ultrasound.
- **Visit 11:** (Day 121 ± 7): On day 11, after embryo transfer, subjects will have a routine pregnancy test (serum β-hCG) to confirm the subject's biochemical pregnancy
- **Visit 12:** (Day 163 ± 7 – Clinical pregnancy confirmation): A transvaginal ultrasound examination will be performed to determine the pregnancy defined as the presence of at least one gestational sac at gestation week 7 ± 1 .
- **Visit 13** (Day 198 ± 7 - End of treatment): A transvaginal ultrasound examination will be performed to determine the Ongoing pregnancy, defined as fetal heartbeats at gestation week 12 ± 1 .

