#### *12.3.3. Secondary outcome*

For continuous variables, results will be shown as mean (SD) and between-group differences will be considered using Student's t-test. For dichotomous outcomes, relative risk (RR) and 95% confidence interval (CI) values will be calculated.

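### Table 2 defines five laboratory endpoints, named as rates in the objectives, as counts without denominators; for oocyte survival the count does not measure cryosurvival

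*Protocol*

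**What the plan says.** The secondary objectives in Section 4.2 list "oocyte survival rate, fertilization rate, embryo-cleavage rate, blastocyst rate, top-quality blastocyst rate, blastocyst survival rate", and the synopsis (Section 2.2) repeats the list. Section 8 then states: "Full details and definitions are provided in Table 2". The rows of Table 2 for these endpoints read as follows.

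- Oocyte survival: "Number of survival oocytes after thawing". The row label itself says number, not rate.
- Embryo-cleavage rate: "Number of embryos on Day 3 after ICSI day".
- Blastocyst rate: "Numbers of embryos on Day 5 and Day 6 after ICSI".
- Top-quality blastocyst rate: the same kind of count, limited to embryos of good quality.
- Blastocyst survival: the number of day-5 and day-6 embryos surviving thaw. Here too the row label says number.

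Other rows of the same table do carry a denominator: fertilization (oocytes injected), premature LH surge (stimulation cycles) and implantation (embryos transferred).

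Three design features bear on these counts. First, Section 5 identifies the last stimulation cycle by a target: "It is defined as a cycle in that the total number of frozen and expected fresh oocytes are at least" 7 ± 1 oocytes. Section 7.3.3 puts the target at more than seven. Second, oocytes from earlier cycles are frozen and later thawed, while those of the last cycle are used fresh. Third, Section 7.3.5 says: "A single embryo will be thawed on the day of embryo transfer". Section 12.3.3 compares continuous secondary outcomes by means and Student's t-test, with no adjustment for a denominator.

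**The concern.** The objectives promise rates and the definitions deliver counts. In a design where every woman had the same number of oocytes thawed and injected, the difference would be cosmetic. Here the number thawed follows from how quickly a woman reaches the target. A woman who reaches it in her first cycle freezes nothing and scores zero survivors, however good the vitrification. A woman who needs three cycles has two cycles' worth of oocytes to thaw.

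Analysed as written, with means and a t-test, the oocyte-survival endpoint would compare how many oocytes were frozen before the last cycle. A difference between arms could then be reported as better or worse cryosurvival when per-oocyte survival is the same. The rationale in Section 3 rests partly on oocyte quantity and quality being comparable between regimens, and these endpoints are meant to bear on that.

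**Working it through.** The protocol gives no figure for these endpoints, so there is none to reproduce. The textual mismatch needs no calculation. The effect of using counts was checked in three steps.

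**1. Oocyte survival, fixed yields.** Assumptions: constant yield per cycle, expected yield equal to actual yield, survival as shown. Survivors = oocytes frozen before the last cycle × survival.

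- Target 7, yield 3, survival 80%: 3+3 = 6 is below 7, so there is a third cycle. Frozen = 6; survivors = 6 × 0.80 = 4.8.
- Target 7, yield 4, survival 90%: 4 is below 7 and 4+4 = 8 reaches it. Frozen = 4; survivors = 4 × 0.90 = 3.6.
- The regimen worse on both yield and survival scores 4.8/3.6 = 1.33 times as high. The rates are 80% and 90%, in the right order.
- At a target of 8 (more than seven) the cycle counts, and so the results, are the same. At a target of 6, the yield of 3 stops after 3+3: frozen = 3, survivors = 3 × 0.80 = 2.4, against 3.6. The order flips with the target alone.

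**2. Oocyte survival, simulation.** Assumptions, none from the protocol: Poisson yield per cycle with a gamma-distributed mean for each woman (shape 4); control mean 3, 3.5 or 4 oocytes per cycle and the other arm 20% lower; 90% survival in both arms; stopping on actual yield. Targets were 6 to 8 and cycle caps 3 to 6. Section 2.4 shows two to three cycles and Section 5 estimates two to four; neither states a hard cap.

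| Setting | Survivor count, lower-yield arm relative to control |
|---|---|
| Target 7, cap 4, mean 3.5 | 3.57 v 3.44, about +4% |
| Target 7, cap 3, means 3 / 3.5 / 4 | −3.7% / −0.5% / +3.3% |
| Target 8, cap 3, same means | −6.7% / −3.9% / −1.1% |
| Target 8, cap 4, same means | −3.0% / +0.3% / +3.7% |
| All settings, one-cycle completion allowed | about −7% to +13% |
| Target 7, cap 4, at least two cycles | −7.6% / −8.1% / −8.9% |
| All settings, at least two cycles | about −14% to −3% |

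The true difference in survival is zero in every row, and survivors divided by oocytes thawed returns 90% in both arms. The largest positive values come from a cap of six cycles, which the protocol does not mention; caps of three and four already give both signs.

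**3. The other counts.** Assumptions: Poisson yields of 3 against 5, target 7, at most 4 cycles, 90% oocyte survival, 70% fertilization, 90% cleavage, 50% of cleaved embryos reaching blastocyst.

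- Day-3 embryos: 4.97 v 5.77 (5.77/4.97 = 1.16).
- Blastocysts: 2.49 v 2.89 (2.89/2.49 = 1.16).
- Blastocysts per cycle: 0.89 v 1.52 (1.52/0.89 = 1.71).

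The target shrinks a gap of about 70% to 16% but keeps its direction. Reversal needs overshoot. With fixed yields of 3 and 4 and 90% survival, oocytes injected are 6 × 0.9 + 3 = 8.4 and 4 × 0.9 + 4 = 7.6. Multiplying by 0.7 × 0.9 gives 5.29 v 4.79 day-3 embryos; halving gives 2.65 v 2.39 blastocysts. Cleavage per 2PN zygote (90%) and blastocysts per 2PN zygote (0.9 × 0.5 = 45%) are the same for both.

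The blastocyst survival count is essentially 0 or 1 at the first thaw, because one embryo is thawed. The single-embryo thaw limits it, not the accumulation target.

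**The case against.** The strongest reply is that these are secondary endpoints, that Section 12.3 promises a detailed analysis plan before data-lock, and that exact denominators are usually fixed there. This would settle the matter if Table 2 were silent. It is not: it states a definition that contradicts the objectives, and an analysis plan would have to override it rather than complete it. That the endpoints are secondary does stand and limits the consequence.

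A reader might go further and infer that the counts favour the poorer regimen, or would flatter dydrogesterone. The documents do not support that. They give no yield per cycle and no hard cycle cap, and the sign of the distortion changes within the schedules they describe. If at least two cycles are required, the lower-yield arm's survivor count is lower in every setting run. Even in the base setting, 3.44 against 3.57 corresponds to z of about 0.9 with 365 women per arm, which is not distinguishable from chance. Nor does the mechanism carry over equally to all five rows, as step 3 shows.

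A reader might also extend the point to the numbers of cumulus-oocyte complexes and MII oocytes. Those are called numbers in both the objectives and Table 2, can be read per retrieval, and stand beside the number of stimulation cycles, itself a secondary endpoint. There is no contradiction there, and singling out first-cycle yield would be a preference rather than a correction.

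**Conclusion.** The definitions are wrong as stated. Five endpoints named as rates are defined as counts, in the table the protocol presents as definitive and in which comparable rows have denominators. That rests on the text alone.

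The consequence is clearest for oocyte survival, where the count reflects yield and number of cycles rather than cryosurvival. Under the assumed yields, with no true difference in survival, it differed between arms by anything from about −14% to +13%; neither sign nor size can be predicted from the protocol. Cleavage and blastocyst counts mainly understate a difference in yield and do not measure embryo development per zygote. The blastocyst survival count carries little information beyond the single thaw. The primary endpoint, ongoing pregnancy after the first transfer, is untouched.

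**What to change.** In Table 2, state a numerator and a denominator for each of the five rows:

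- Oocyte survival: oocytes surviving / oocytes warmed, among women with any oocytes warmed.
- Embryo cleavage: day-3 embryos / 2PN zygotes.
- Blastocyst and top-quality blastocyst: day-5/6 blastocysts (of any quality, and of top quality) / 2PN zygotes.
- Blastocyst survival: blastocysts surviving / blastocysts warmed.

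The counts may stay as descriptive results. The two survival labels should match the objectives.

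The cost is a rewording of Table 2, with the ethics review that Section 1 requires for any amendment; no clinical procedure changes. Sections 7.3.3 to 7.3.5 describe the survival, 2PN and embryo assessments needed, but the case report form is not shown, so it should be checked that the number warmed is captured. One limitation should be stated: women who finish in one cycle contribute nothing to oocyte survival, so that rate compares subsets formed after randomization. Because the trial is open-label, the denominators should be settled before outcome data by arm are examined.
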